#### **D.** Safety Endpoints

- i. Adverse events (AEs) particularly GI related adverse events, abnormal liver function tests.
- ii. Percent of patients (males only) with development of Testicular adrenal rest tumors (TART) at pubertal onset and adult height

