### Secondary Objectives

- To assess the safety and tolerability of antiandrogen, aromatase inhibitor and reduced hydrocortisone dose combination therapy.
- To assess the effect of antiandrogen, aromatase inhibitor and reduced hydrocortisone dose combination therapy on height gain, growth velocity and bone maturation prior to puberty.
- To assess the effect of antiandrogen, aromatase inhibitor and reduced hydrocortisone dose combination therapy on height gain and bone maturation during puberty
- To assess the effect of antiandrogen, aromatase inhibitor and reduced hydrocortisone dose combination therapy on development of TART in males and establishment of menstrual regularity in females
- To assess the effect of antiandrogen, aromatase inhibitor and reduced hydrocortisone dose combination therapy on fasting glucose, body mass index, and bone mineral density
- To assess hormonal control based on percent of visits within the normal (or optimal) range for 17OHP, androstenedione, PRA and ACTH
- To assess sex differences in outcomes.

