# **B** Secondary Endpoints

Secondary outcome variables will be examined between the two study arms at baseline, pubertal onset and adult height (final visit). To examine sex differences, the secondary outcomes variables will be examined by-sex between the two study arms.

'Pubertal Onset' is defined as the visit when patients entered puberty (Tanner 2 breast in females, testicle size > 3mL) or completed therapy with the aromatase inhibitor and or LHRHa.

- i. Adult height achieved will also be expressed standard deviation (SD) units and in cm as the difference in height achieved in relation to their target height (i.e., mid-parental height, calculated based on their parental heights)
- ii. Height achieved (SD units) from baseline to pubertal onset
- iii. Height achieved (SD units) from pubertal onset to adult height
- iv. Predicted adult height (using Bayley-Pinneau method) at pubertal onset
- v. Predicted adult height (using Bayley-Pinneau method) change from baseline to pubertal onset
- vi. Predicted adult height (using Bayley-Pinneau method) change from pubertal onset to final height
- vii. Growth velocity (in SD units) from baseline to pubertal onset
- viii. Growth velocity (in SD units) from pubertal onset to adult height
- ix. Percent of visits with ACTH in normal range from baseline to pubertal onset
- x. Percent of visits with ACTH in normal range from pubertal onset to adult height
- xi. Percent of visits with androstenedione in normal range from baseline to pubertal onset
- xii. Percent of visits with androstenedione in normal range from pubertal onset to adult height
- xiii. Percent of visits with 17-hydroxyprogesterone in the optimal range (<1,200 ng/dL) or high (>1,200 ng/dL) from baseline to pubertal onset
- xiv. Percent of visits with 17-hydroxyprogesterone in the in the optimal range (<1,200 ng/dL) or high (>1,200 ng/dL) from pubertal onset to adult height
- xv. Percent of patients with onset of central precocious puberty (CPP)

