(6) A leuprolide stimulation test, to assess pubertal status of the hypothalamic-pituitarygonadal axis will be performed at the first visit and all subsequent visits after the child has reached a bone age of 10 in boys or 9 in girls, or if there is clinical suspicion of hypothalamic-pituitarygonadal activation (i.e. testicular enlargement in boys, breast tissue in girls). Children who are started on an LHRH analog for central precocious puberty and those who switch LHRH analog medication type will have leuprolide stimulation test performed 3 months after beginning treatment to confirm efficacy of this treatment. Additional leuprolide stimulation testing while receiving an LHRH analog will only be done if clinically indicated. This testing will resume once the patient is taken off LHRH analog therapy. Measurement of gonadotropins by third-generation immunochemiluminometric assays (ICMA) will be done. Blood withdrawal: 12 mL.

(7) Measurement of plasma 17-hydroxyprogesterone, DHEA-S, androstenedione, estradiol, testosterone, cortisol, and ACTH, estradiol starting as near 0800 h as feasible. The morning hydrocortisone dose will be held until after these samples have been obtained. Blood withdrawal: 18 mL.

(8) Blood to be frozen for possible future hormone measurements: 17 mL.

(9) Upright and supine plasma renin activity. Blood withdrawal: 14 mL.

(10) Routine CBC, thyroid panel and SMAC. Blood withdrawal: 8 mL.

(11) One-hour cortrosyn (ACTH) test to assess levels of steroid intermediates in response to ACTH stimulation. Cortisol, 17-hydroxyprogesterone, androstenedione, and DHEA will be measured at time 0 and 60 minutes after ACTH bolus infusion. Blood withdrawal: 24 mL. This test will be performed at the beginning and end of the study, and, if indicated, at some other visits.

(12) Fasting glucose, insulin and leptin levels. Blood withdrawal: 5 mL.

(13) Lipid profile. Blood withdrawal: 2.5 mL.

(14) Plasma and urinary catecholamines and metanephrines Blood withdrawal: 20 mL.

(15) Bone densitometry (DEXA): to be performed at start of treatment, annually thereafter (e.g., every other NIH visit), and at attainment of final adult height, to measure bone density of the forearm, femoral neck, and spine (AP and lateral).

(16) MRI abdomen: to be performed after 2-3 years on the protocol and after the patient's 6th birthday.

(17) Boys will have a testicular ultrasound and girls will have a pelvic ultrasound done

each visit.

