### Treatment of Testicular Adrenal Rest Tissue or Macronodular Disease.

Testicular ultrasound is a sensitive method for detecting testicular adrenal rest tissue; however, testicular ultrasounds are not routinely done on CAH patients and the incidence of adrenal rest tissue with this sensitive method is unknown. Typically, testicular adrenal rests are thought to be evidence of poor control, but this may only be the case if significant growth occurs. If a small amount of adrenal rest tissue is present, and there is no growth over time, a change in treatment may not be necessary. Our studies of male patients with CAH support this approach [41]. If interval growth occurs between visits (i.e. over 6 months), glucocorticoid dose will be increased 20%, or to a minimum of 12 mg/m2/day in the flutamide-aromatase inhibitor group. If interval growth occurs on a hydrocortisone dose of at least 12 mg/m2/day in the flutamide-aromatase inhibitor treatment group, or 18 mg/m2/day in the conventional treatment group, then a 10-day course of dexamethasone (15 mcg/kg/day given qhs) will be instituted. Flutamide and aromatase inhibitor therapy will be continued.

If the rare occurrence of adrenal macronodular disease develops, a 10 day course of dexamethasone (15 mcg/kg/day given qhs) will be instituted. Subsequently, glucocorticoid dose will be increased to a minimum of 12 mg/m2/day in the flutamide-aromatase inhibitor treatment group, and flutamide and aromatase inhibitor therapy will be continued. Glucocorticoid dose will be increased to a minimum of 15 mg/m2/day in the conventional treatment arm.

The boy with significant testicular adrenal rest tissue and the patient who is developing macronodular enlargement represent special cases in which it may not be appropriate to restrict hydrocortisone dosage to the physiologic range. Fortunately, this is a small proportion of patients with CAH. We recognize that the final analysis of the data will need to take account of these subgroups.

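### Safety endpoint D.ii names only two visits for TART although boys are scanned every six months; it should count TART on any scheduled ultrasound.

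*Combined protocol and SAP*

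**What the plan says.** Item ii of section D (Safety Endpoints) sets the outcome as "Percent of patients (males only) with development of Testicular adrenal rest tumors (TART) at pubertal onset and adult height". The matching secondary objective is to assess the effect of the regimen "on development of TART in males and establishment of menstrual regularity in females", with no time point attached.

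The first named visit is defined under Secondary Endpoints: "Pubertal Onset' is defined as the visit when patients entered puberty" (in boys, testes above 3 mL) "or completed therapy with the aromatase inhibitor and or LHRHa". The second is the visit at which growth over 12 months has fallen below 1.5 cm.

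The Protocol section brings subjects in every six months until adult height. Item 17 of its evaluation list says "Boys will have a testicular ultrasound and girls will have a pelvic ultrasound done" at each visit. The section on testicular adrenal rest tissue then acts on what the scans show: "If interval growth occurs between visits (i.e. over 6 months), glucocorticoid dose will be increased 20" per cent, or to a stated minimum in the investigational arm. If growth occurs at or above a dose that differs by arm, "a 10-day course of dexamethasone (15 mcg/kg/day given qhs) will be instituted". The Précis and the Protocol section end the investigational regimen in boys at about age 14, after which they receive conventional treatment.

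Nowhere in the text reviewed is there an any-visit count, a time to first detection, a rule for boys with rests at baseline, or a rule for rests that were treated. The rest-tissue section says only that the final analysis must allow for boys with significant rest tissue.

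**The concern.** The objective is about development of TART, which is incidence. The endpoint, taken at its word, is presence at two visits. Between those visits the protocol looks for rests every six months and treats the ones that grow, so a reading can come after treatment. The second reading also comes after boys have left the regimen whose safety is in question.

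Two kinds of event can be missed or misplaced. A rest that appears and resolves between the named visits is not counted. A rest that first appears after an early pubertal onset but before age 14 arises on the regimen, yet is read only at adult height, off the regimen.

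What is at stake is whether the trial can say how often rests develop under restricted hydrocortisone. The protocol itself says that the incidence of rest tissue by this sensitive method is unknown, so the serial scans are among its more informative safety data.

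**Working it through.** **Plan's own figure.** There is none for TART. The only power figures, 24 and 17 per group, concern adult height. They reproduce (two-sample t-test, SD 6 cm, 80% power, two-sided 5%: 23.6 for 5 cm and 16.7 for 6 cm) but do not bear on this point.

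**Scans taken and scans used.** Visits are six-monthly and the regimen ends at about 14 (Protocol section). Entry at age 4-10 and adult height at 16-18 are my assumptions.
- Scans by age 14: 2 × (14 − 10) = 8 to 2 × (14 − 4) = 20.
- Scans by adult height: 2 × (16 − 10) = 12 to 2 × (18 − 4) = 28.
- Share used by a two-visit endpoint: 2/28 = 7% to 2/12 = 17%.
- Time off-regimen at the second reading: 16 − 14 = 2 to 18 − 14 = 4 years. The documents state no duration.

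**Early puberty.** If a boy's testes exceed 3 mL at 12 (assumed) and that sets his pubertal-onset visit, 2 × (14 − 12) = 4 later scans run up to the age-14 visit. A rest first seen on one of these enters the endpoint only if it is still present at adult height.

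**What two readings capture (illustration).** All inputs here are assumed: no rests at baseline; a chance h per six-month interval that a rest appears; a chance r per interval that a present rest resolves; 14 scans up to the first reading and 6 more to the second; h and r constant throughout.
- Ever positive: 1 − (1 − h)^20.
- Present t visits after being absent: P(t) = h/(h + r) × [1 − (1 − h − r)^t].
- Positive at either reading: P(14) + [1 − P(14)] × P(6).

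With h = 2% and r = 10%:
- Ever positive = 1 − 0.98^20 = 0.332.
- P(14) = 0.1667 × (1 − 0.88^14) = 0.139.
- P(6) = 0.1667 × (1 − 0.88^6) = 0.089.
- Either reading = 0.139 + 0.861 × 0.089 = 0.216.
- Share captured = 0.216/0.332 = 65%.

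| r per interval | Share captured, h = 1-3% | Boys counted of 5.0 ever positive (15 boys, h = 2%) |
|---|---|---|
| 0 | 100% | 5.0 |
| 10% | 63-66% | 3.2 |
| 25% | 38-41% | 2.0 |
| 50% | 21-24% | 1.1 |

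Fifteen boys per arm is also assumed (half of the planned 30). An any-scan count captures every boy ever positive in this model. The loss is governed almost entirely by r, about which the documents say nothing.

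**The case against.** The strongest reply is that the wording need not mean a snapshot. Development is an incidence word, and the phrase can be read as TART developed by each visit, in which case a treated boy is counted. That reading is plausible. It shows that the rule needs to be written down, not that it has been.

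Second, nothing in the documents says that treated rests regress. The rest-tissue section acts on growth and allows small stable rests to be left alone, and such rests would still be visible at both readings. This stands: with r = 0 nothing is lost.

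Third, some information is captured elsewhere. Hydrocortisone dose and cumulative glucocorticoid exposure are secondary endpoints, adverse events are a safety endpoint (naming gastrointestinal events and liver tests in particular), and a safety committee reviews the data yearly. None of these gives a count of boys with TART. The analysis section also refers to an SAP in Appendix A that was not in the text reviewed; a counting rule there would settle the matter.

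A reader might go further and infer that the endpoint is biased toward no difference between arms. The documents do not support that. Suppose 5 of 15 boys on the regimen and 2 of 15 on conventional treatment ever develop TART, and count only the rests that do not regress:
- No regression: 33% against 13%.
- 60% regression on the regimen only: 2/15 against 2/15, 13% each.
- 60% in both arms: 2/15 against 0.8/15, 13% against 5%, with the 2.5:1 ratio intact.
- 60% in the conventional arm only: 5/15 against 0.8/15, 33% against 5%.

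The direction follows from the assumption alone. Nor are both readings taken after the regimen has stopped: the pubertal-onset reading falls on the regimen or at its end. And although the protocol reports that rests are typically taken as a sign of poor control, it adds that this may hold only where they grow significantly.

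**Conclusion.** The point holds as a defect in the endpoint definition. Two visits are named where 12 to 28 scans would exist (assumed entry and adult-height ages), one of the two is normally off-regimen, and no rule says how interim or treated rests count. Read literally, the endpoint does not measure development of TART on the regimen.

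Its effect on the result cannot be sized from the documents. Under the assumptions above, the share of affected boys captured runs from 100% with no regression to 21-24% with 50% regression per interval. The documents do not establish a bias in favour of either arm. The case for change rests on clarity and on using scans already scheduled.

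**What to change.** Redefine safety endpoint D.ii as the percent of boys, free of rest tissue at baseline, with TART on any scheduled testicular ultrasound from randomisation, by arm, with age at first detection. Split it at the age-14 visit, using the protocol's own rule of the study visit nearest the birthday. In addition:
- report boys with rest tissue at baseline separately;
- distinguish rests with interval growth from small stable ones;
- give the number of scans, or follow-up time, per arm as denominator;
- tabulate by arm the boys who had the glucocorticoid increase or dexamethasone course for rest tissue;
- keep prevalence at pubertal onset and adult height as supplementary.

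The cost is endpoint wording and tabulation of ultrasound reports already scheduled. No procedure and no clinical rule changes. There are drawbacks. Reported rates may rise, and small stable rests that the protocol regards as possibly unimportant are included. The count also depends on scans attended: missed radiology is not reported as a deviation, and subjects who leave the study are asked only for home heights and one final height and weight visit. That is why the denominator must be shown.

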#### **Study Design and Methods**

#### **Patient Selection**

Subjects will be boys with bone ages 2 to 13 years and girls with bone ages 2 to 11 years with classic 21-hydroxylase. Subjects must either not yet have undergone pubertal activation of the hypothalamic-pituitary-gonadal axis, or, if pubertal activation has occurred, must be receiving an LHRH agonist to suppress their secondary central precocious puberty. This requirement is to ensure that growth during the study will not be compromised by secondary central precocious puberty. Children with a bone age of 1 to 2 years may enroll in the protocol for optimization of conventional therapy as described below, but will not be randomized to a study arm until the bone age reaches 2. Monitoring of such children will be identical to older children randomized to the conventional arm.

Exclusion criteria include children who have concurrent illnesses requiring glucocorticoid treatment (such as severe asthma), or requiring drugs that markedly alter hydrocortisone metabolism (such as anticonvulsants), and children who cannot be brought into reasonable control with conventional treatment (an unusual occurrence).

#### **Protocol**

Before entry into the study, adequacy of the patient's CAH management will be documented. Treatment will be modified as needed to achieve optimal control, according to state-of-the-art concepts of CAH management, as outlined below.

Secondary central precocious puberty will be defined by meeting one or more of the following criteria:

1) Peak Leuprolide-stimulated LH/FSH ratio consistent with central puberty.

3) Baseline LH-ICMA of greater than 0.3 [35].

4) Clinical evidence of central precocious puberty (breast development in girls and testicular enlargement in boys).

Patients who are in secondary central precocious puberty will be offered treatment with a commercially available LHRH agonist, Lupron Depot(administered via monthly intramuscular injection, TAP) or an investigational LHRH agonist, Deslorelin (administered via daily subcutaneous injection). Since 1979, Deslorelin has been used at the NIH for the treatment of

central precocious puberty and has been shown to be safe and effective [35]. Other commercially available products include Histrelin (Roberts) and Lupron Injection, both administered via daily subcutaneous injection. We have chosen to continue to use Deslorelin because it is readily available through the NIH Pharmacy (there was a recent shortage of Histrelin), it is less expensive than the commercially available subcutaneous products, and we have extensive personal experience in its use.

Choice of medication will be based on patient and family preferences. Families will be counseled on the advantages and disadvantages of these two therapies. Both medications are known to effectively suppress the hypothalamic-pituitary-gonadal axis. Known side effects include rash, and local injection site reactions (milder with Deslorelin). Lupron has the advantage of monthly administration and the disadvantage of an increase risk of local injection site abscess formation (Deslorelin may cause redness at the injection site but has not been reported to result in abscess formation). Lupron also may require more dose adjustments in the beginning of therapy. Anaphylactoid reactions are an extremely rare risk for both medications. Children will return to the NIH day hospital 3 months after starting LHRH analog therapy for evaluation of hypothalamic-pituitary-gonadal suppression. Those patients who are currently being treated with Deslorelin (previously under protocol 79-CH-112) will be continued on Deslorelin or switched to Lupron, depending on patient preference.

Once degree of CAH control has been judged optimal, children will be randomized to receive either the regimen of flutamide, testolactone or letrozole, and reduced hydrocortisone dose or conventional treatment (with hydrocortisone and fludrocortisone) until the age of 13 in the girls and 14 in the boys. At that time the regimen of flutamide, testolactone, and reduced hydrocortisone dose will be discontinued in boys so that the subjects can progress through puberty. At age 13 years, girls who are receiving flutamide and testolactone or letrozole therapy will discontinue the aromatase inhibitor therapy (to allow normal progression of puberty) and continue flutamide (to continue androgen blockade). Flutamide therapy will continue until 2 years after menarche or when final height is reached, whichever occurs first.

Children who are also receiving concurrent LHRH analog to suppress central puberty will also discontinue this agent at age 13 in the girls or age 14 in the boys. The operational definition of age 13 or 14 will be the NIH study visit that is closest to their thirteenth or fourteenth birthday. The operational definition of attainment of final height, as in our other long-term trials, will be the study visit at which the incremental growth over the previous 12 months declines to less than 1.5 cm (0.6 inch).

During flutamide and aromatase inhibitor treatment hydrocortisone dose will be decreased in 4 equal weekly steps to approximately 8 mg/m^2/day. During this month close contact will be maintained with the family by telephone and/or outpatient visits (for local patients), or referring physician visits (for distant patients), to check for symptoms or signs of adrenal insufficiency. If the hydrocortisone dosage of approximately 8 m^2/day produces symptoms or signs of adrenal insufficiency in any subject, the dosage will be adjusted on an individual basis to a dosage that will not cause symptoms or signs of adrenal insufficiency.

Patients will initially be placed on Testolactone 20 mg/kg/day of testolactone. The dose will then be increased at weekly intervals to 30 and then 40 mg/kg/day, which will be the maximum dose for the study (approximately equivalent to the usual maximal adult dose of 2 grams per day).

Patients placed on letrozole will receive a dose comparable to the dose used to suppress estrogens in adult women (1.5 mg per square meter of body surface area). This is the same dose of letrozole used for the treatment of girls with McCune Albright Syndrome.

Flutamide will also be administered in increasing doses. Patients will initially be placed on 5 mg/kg/day of flutamide. The dose will then be increased at weekly intervals to 7.5 and then 10 mg/kg/day, which will be the maximum dose for the study. This is approximately the same dose used to treat men with prostate cancer (750 mg/day, or about 10 mg/kg/day).

Subjects will be evaluated as outpatients, day-hospital patients, or inpatients on the pediatric endocrine ward at 6-month intervals until final adult height is attained. The following evaluations will be made:

- (1) Ten standing height measurements by stadiometer.
- (2) Ten sitting height measurements.
- (3) Weight.
- (4) Bone age.
- (5) Two 24-hour urine collections for cortisol.

(6) A leuprolide stimulation test, to assess pubertal status of the hypothalamic-pituitarygonadal axis will be performed at the first visit and all subsequent visits after the child has reached a bone age of 10 in boys or 9 in girls, or if there is clinical suspicion of hypothalamic-pituitarygonadal activation (i.e. testicular enlargement in boys, breast tissue in girls). Children who are started on an LHRH analog for central precocious puberty and those who switch LHRH analog medication type will have leuprolide stimulation test performed 3 months after beginning treatment to confirm efficacy of this treatment. Additional leuprolide stimulation testing while receiving an LHRH analog will only be done if clinically indicated. This testing will resume once the patient is taken off LHRH analog therapy. Measurement of gonadotropins by third-generation immunochemiluminometric assays (ICMA) will be done. Blood withdrawal: 12 mL.

(7) Measurement of plasma 17-hydroxyprogesterone, DHEA-S, androstenedione, estradiol, testosterone, cortisol, and ACTH, estradiol starting as near 0800 h as feasible. The morning hydrocortisone dose will be held until after these samples have been obtained. Blood withdrawal: 18 mL.

(8) Blood to be frozen for possible future hormone measurements: 17 mL.

(9) Upright and supine plasma renin activity. Blood withdrawal: 14 mL.

(10) Routine CBC, thyroid panel and SMAC. Blood withdrawal: 8 mL.

(11) One-hour cortrosyn (ACTH) test to assess levels of steroid intermediates in response to ACTH stimulation. Cortisol, 17-hydroxyprogesterone, androstenedione, and DHEA will be measured at time 0 and 60 minutes after ACTH bolus infusion. Blood withdrawal: 24 mL. This test will be performed at the beginning and end of the study, and, if indicated, at some other visits.

(12) Fasting glucose, insulin and leptin levels. Blood withdrawal: 5 mL.

(13) Lipid profile. Blood withdrawal: 2.5 mL.

(14) Plasma and urinary catecholamines and metanephrines Blood withdrawal: 20 mL.

(15) Bone densitometry (DEXA): to be performed at start of treatment, annually thereafter (e.g., every other NIH visit), and at attainment of final adult height, to measure bone density of the forearm, femoral neck, and spine (AP and lateral).

(16) MRI abdomen: to be performed after 2-3 years on the protocol and after the patient's 6th birthday.

(17) Boys will have a testicular ultrasound and girls will have a pelvic ultrasound done

each visit.

(18) Photographs will be taken with the patient wearing a bathing suit or underwear. This will be done at the beginning of the study and then yearly thereafter.

(19) If clinically indicated, an adrenal ultrasound and/or an additional MRI of the abdomen and adrenals may be done at follow-up visits.

(20) An apparent cortisol metabolic clearance rate determination will be performed in all patients. In patients in the flutamide-testolactone treatment group, this test will be performed twice, once off flutamide and testolactone and once on flutamide and testolactone.

Determining the apparent cortisol metabolic clearance rate in our CAH patients will enable us to determine if a patient's dose of hydrocortisone is related to their metabolic clearance of cortisol and if flutamide and/or testolactone interfere with the metabolic clearance of hydrocortisone. Cortisol metabolic clearance rate will be determined by infusing hydrocortisone overnight, starting at 6:00 p.m. and ending the hydrocortisone infusion at 2:00 a.m., at an infusion rate of 0.6 mg/m2/hour. Oral hydrocortisone will be withheld on the day of testing. This testing will be done at the randomization visit for all new patients. Patients already on flutamide and testolactone will have one of their visits extended by 3 days in order to perform this testing on and off flutamide and testolactone.

(21) Psychological assessment will be performed at baseline and completion of the study. The following standard tests will be performed: Wechsler Intelligence Scale to determine IQ, California Verbal Learning Test to evaluate verbal-memory skills, Woodcock Johnson Achievement Tests to identify learning disabilities, Bender-Gestalt Test to evaluate visual-motor skills and Continuous Performance Test to evaluate attention. Additional testing may be performed if clinically indicated. If desired, a report will be provided to the parents for potential use by the child's school. Patients will be invited to participate in an NIMH study involving magnetic resonance imaging of the brain to examine the effects of androgen exposure on brain morphology. The proposed psychological assessment will augment this data. We plan to collect data prior to the onset of puberty and after puberty.

Many children with CAH enrolled in 96CH003 are in special education classes or have documented language or perceptual delays by parental report. Learning disabilities are 6 times more likely to occur in males than females. The role of androgens in this phenomenon is unknown. Sex differences in patterns of brain maturation in children have been found [36]. This sexual dimorphism is of interest in light of the differences in prevalence, age of onset, and symptomatology noted in nearly every neuropsychiatric disorder of childhood onset. Sexually distinct patterns of normal brain development may be due to the X or Y chromosomes, effects of hormones, or environmental factors. Several studies on CAH children have suggested that CAH females are similar to males in both their behavior and/or cognition. For example, a study of CAH control females with equivalent general intelligence found CAH patients to have inferior verbal vs. visual and arithmetic scores typical of male vs. female differences [37]. CAH females have been shown to have improved spatial skills, typical of males [38]. Studies of gender-related behavior have shown that CAH females have more masculine type orientation than their unaffected sisters [39] and have more masculinized play preferences [40]. These type of data have been interpreted as a consequence of early in utero androgen exposure since testosterone is known to promote development of the right hemisphere and delays maturation of the left hemisphere. We hypothesize that in CAH females, the organization of the brain is more like males than females, while CAH boys are more like unaffected males.

(22) At the time of menarche, girls will be asked to keep a calendar documenting their menstrual history.

Due to the known hepatotoxicity of flutamide in some patients (see Risks below), patients who randomize to the flutamide and aromatase inhibitor arm will have liver function tests drawn by their local physician every 2 weeks for the first 3 months, then once a month for the next 9 months, then every 3 months for the duration of the study. Parents will also be carefully instructed about the signs and symptoms of liver toxicity and the procedure to follow if such symptoms occur (see consent). We have not, however, observed flutamide-associated liver toxicity in any child receiving flutamide during our initial 6-month pilot study or the ongoing current study.

If a patient develops premature pubertal activation of the hypothalamic-pituitary-gonadal axis during the study, he or she will receive treatment with an LHRH analog. Since we cannot predict with certainty who may develop secondary central precocious puberty during the study, all patients and their families will receive an explanation of the use of LHRH analogs and available treatment regimens. If a child develops premature pubertal activation of the hypothalamic-pituitary-gonadal axis, the NIH will supply a commercially available LHRH agonist, Lupron (monthly intramuscular injection) or an investigational LHRH agonist, Deslorelin (daily subcutaneous injection) Choice of medication will be based on family preference and demonstrated efficacy in each patient.

Because the degree of control of CAH often varies over time for unexplained reasons, adjustments in total hydrocortisone dose will be permitted during the conventional treatment arm throughout the study, as would be the case in clinical practice. These dose adjustments will be guided by both clinical and biochemical criteria as outlined in the following discussion of the principles that are currently used in managing these patients.

